5 GENERAL STATISTICAL METHODS

5.1 SAMPLE SIZE JUSTIFICATION

Sample size was based on the number of participants who enrolled in the parent study and subsequently received doses of fitusiran while enrolled in the LTE14762 study, and not on statistical considerations.

5.2 GENERAL METHODS

Both efficacy and safety analysis under the original and revised dose regimens will be analyzed separately, unless otherwise specified. The data collected during the 2020 voluntary dose pause will be analyzed along with the pre-pause data.

A significant dose is defined as any single dose of fitusiran that is greater than or equal to 20 mg. Before the voluntary dose pause, the analysis period for efficacy endpoints starts from the date of first significant dose up to the earlier of 2020 voluntary dose pause date or the last day of study follow-up. For safety endpoints, the analysis will be performed based on LTE14762 study period data only up until the dose restart date. Date of first significant dose in the TDR14767(ALN-AT3SC-001) and LTE14762 study/studies will be designated as Treatment Day 1; there will be no Treatment Day 0. Participants who receive doses (either weight-dependent or weight-independent) of at least 20 mg but less than 75 mg will be “classified” as “50 mg” participants, while participants receiving doses of greater than or equal to 75 mg will be “classified” as “80 mg” participants (except PK analysis in which actual dose on Day of PK sample collection will be used). However, for purposes of efficacy and safety analyses and summaries in the final CSR report for the LTE14762 study, the classification of each participant under the original dose and regimen will be according to the fixed dose to which they are eventually taken by the end of the LTE14762 study original dose period. For example, participants who received a 50 mg dose in TDR14767(ALN-AT3SC-001) or LTE14762 and then were switched to 80 mg dose at some point in time during the LTE14762 study, are classified in the LTE14762 study as “80 mg” participants (except for PK analyses). Treatment after the volunteer dose pause will be treated as each participant’s treatment sequence.

[figure not shown]
Treatment Days under the original dose and regimen will be calculated as evaluation date – first significant dose date +1 and pre-treatment days will be calculated as evaluation date – first significant dose date. (The pre-treatment day formula applies when evaluation date < first significant dose date; ie, for example, there will be pre-treatment Days ... -3, -2, -1, then treatment Day 1, 2, 3, 4, ...; there is no “pre-Treatment Day 0” nor is there any “Treatment Day 0”).

We also define Study Days in the LTE14762 study as the number of days from first significant dose in LTE14762 and calculate similarly as the Treatment Days. For participants who received first significant dose in LTE14762, the Study Days is the same as the Treatment Days.

For participants under the revised dose and regimen, both efficacy and safety data will be analyzed from the dose re-start Day 1 up until the last day of study follow-up.

Treatment day after the dose re-start will be calculated as evaluation date – first dose date after dose re-start + 1 (days). It should be not applicable for assessments before the dose re-start. A summary of study periods and start day in analysis is outlined in [Figure 1](#)

Figure 1 Study periods and analysis start day summary

	Original dose and regimen	2017 clinical hold/2020 voluntary dose pause	Revised dose and regimen
Efficacy analysis	Starts from first significant dose of fitusiran in TDR14767(ALN-AT3SC-001) or LTE14762 and in terms of treatment days.	Starts from the 29th days after last dose date before the hold/pause	Starts from first dose date of revised dose and regimen and in terms of treatment days
Safety analysis	Starts from first significant dose of fitusiran in LTE14762 and in terms of study days	Starts from the day after last dose date before the hold/pause and in terms of study days	Starts from first dose date of revised dose and regimen and in terms of study days

Summary statistics will be reported by analysis visits defined in [Section 5.10](#) below. Unless otherwise noted, tables under both the original and revised dose regimens will be presented by hemophilia type, inhibitor type and overall. Participants who received a significant dose in TDR14767(ALN-AT3SC-001) will be considered as a subgroup in the analysis under the original dose and regimen. Details will be specified in the [Section 6.11](#).

Categorical data summary will include the number and percentage of participants within each category, with a category for missing data. Continuous data summary will include descriptive statistics - the number of participants, mean, median, standard deviation (SD), first quartile (Q1), third quartile (Q3), minimum, and maximum. The precision of the measurement for each continuous variable will be used to determine the number of decimal places to present in tables, figures and derived listings. Minimum and maximum values will be reported with the same

precision as the units of measure. The other statistics will be reported with 1 greater decimal place. Any values that require transformation to standard units (metric or SI) will be converted with the appropriate corresponding precision.

To be consistent with the compound level wording, ‘revised dose and regimen’ will be shown as ‘recommended dose and regimen’ in the statistical output.

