10.2 STATISTICAL METHODOLOGY

All study data will be presented in by-patient data listings. Statistical analyses will be primarily descriptive. Summary tables will be presented by starting dose level and final dose level/frequency of fitusiran separately for patients with and without inhibitors.

For categorical variables, summary tabulations of the number and percentage of patients within each category (with a category for missing data) will be presented. For continuous variables, the number of patients, mean, median, standard deviation, minimum, and maximum values will be presented.

All analyses will be conducted for patients with and without inhibitors separately.

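### In dose-labelled summaries of the original dose period, events before a dose switch are counted under the later dose, and the protocol's starting-dose tables are dropped without being listed

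*SAP*

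**What the plan says.** SAP 5.2 first sorts participants by dose received: at least 20 mg but under 75 mg is the 50 mg class, and 75 mg or more is the 80 mg class. It then overrides this "for purposes of efficacy and safety analyses and summaries in the final CSR report for the LTE14762 study". For those outputs the rule is that "the classification of each participant under the original dose and regimen will be according to the fixed dose to which they are eventually taken"; the reference point is the close of the period before the pause. Its own example takes people given 50 mg at first: those who "then were switched to 80 mg dose at some point in time during the LTE14762 study, are classified in the LTE14762 study as" belonging to the 80 mg class.

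Other parts of SAP 5.2 set the limits of the rule:

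- PK is exempt: "except PK analysis in which actual dose on Day of PK sample collection will be used".
- For efficacy, "the analysis period for efficacy endpoints starts from the date of first significant dose", which may lie in the parent study.
- For safety, "the analysis will be performed based on LTE14762 study period data only up until the dose restart date".
- After the pause a different scheme applies: "Treatment after the volunteer dose pause will be treated as each participant’s treatment sequence".
- Unless otherwise noted, table columns are hemophilia type, inhibitor type and overall.

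Protocol 10.2 states: "Summary tables will be presented by starting dose level and final dose level/frequency of fitusiran separately for patients with and without inhibitors". Protocol 10.2.6 adds that treatment-emergent adverse events are to be shown for each dose level as well as overall.

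**The concern.** The final-dose label depends on something that happens after follow-up begins, yet it is attached to all of that follow-up. A participant who spends time at one dose and then moves brings his earlier bleeds, adverse events and days into the column for the dose he moved to. He must also stay on study long enough to be switched, so early person-time is sorted by a future event.

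Dose matters to the safety reading. Protocol 1.5 and 1.6 tie thrombotic risk to low antithrombin, and Protocol 1.3.3 describes antithrombin reduction as dose-related. A dose-labelled table of thrombosis or liver events is therefore one that readers will look at closely. The by-year ABR in SAP 6.3.1.1 is meant to show durability. If it were shown by dose, the early years of an 80 mg column could contain lower-dose time, and a falling ABR could partly reflect a dose increase.

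The starting-dose table that the protocol pairs with the final-dose table would let a reader see this. The SAP does not define it.

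**Working it through.** **1. Does anything in the SAP separate time before and after a switch?**

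- SAP 6.3 lists the periods removed from the on-treatment analysis: dose interruptions, surgery and trauma, antithrombin treatment, and time after emicizumab. A dose change is not among them.
- SAP 6.3.1.1 divides a participant's bleeds by his days in the period. All bleeds and days that remain in the period count.
- Efficacy time can start in the parent study, so parent-study bleeds after the first dose of at least 20 mg are carried along. Safety uses extension-study data only, so parent-study adverse events are not carried along, but extension-study events before a switch are.

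No step splits a participant at the switch.

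**2. Is the missing starting-dose view listed as a change?** SAP 2.7 lists one departure from the protocol's statistics, the start of the analysis periods. SAP 2.5 and 2.6 do not mention starting-dose tables either.

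**3. One participant (invented figures, to show the mechanism).** One year on 50 mg with 4 bleeds, then three years on 80 mg with 3 bleeds:

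- by dose in force: 4/1 = 4.0 on 50 mg and 3/3 = 1.0 on 80 mg;
- under the SAP rule: (4 + 3)/(1 + 3) = 1.75, labelled 80 mg.

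This is one person's ABR. If he joins 20 others with an ABR of 1.0, the group mean is (20 + 1.75)/21 = 1.04.

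**4. Group scale.** There is no plan figure to reproduce. The one input from the documents is the 80 mg group size, N = 21, from the August 2017 snapshot in Protocol 1.3.3 (50 mg: N = 13). It is not the final classification. Assumed: k switchers from 50 to 80 mg, a fraction f of their follow-up on 50 mg, equal follow-up for all, and true rates r50 and r80.

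Share of 80 mg person-time really on 50 mg: s = (k/21) × f.

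Reported 80 mg ABR = (1 − s) × r80 + s × r50.

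| k | f | s | ABR if r50 = 3, r80 = 1 | ABR if r50 = 2, r80 = 1 | ABR if both = 1 |
|---|---|---|---|---|---|
| 2 | 0.10 | 1.0% | 1.02 | 1.01 | 1.00 |
| 5 | 0.25 | 6.0% | 1.12 | 1.06 | 1.00 |
| 10 | 0.50 | 23.8% | 1.48 | 1.24 | 1.00 |

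These are crude means. The planned negative binomial estimate, adjusted for baseline ABR, would not match them exactly.

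**5. Adverse events.** Suppose each switcher has a 10% chance of a given event while on 50 mg and none later. The 80 mg column then gains k × 0.10/21, which is 1.0, 2.4 or 4.8 percentage points for k = 2, 5 or 10. This is an upper figure, because a switcher who also has the event on 80 mg would be counted there anyway.

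**The case against.** The strongest reply is that SAP section 6 specifies no ABR or adverse event table by 50 or 80 mg for the original period. The default columns are not by dose, and a dose label cannot change an overall, hemophilia-type or inhibitor column. This stands, and it limits the point to dose-labelled output. It does not remove the point. SAP 5.2 defines the dose classes expressly for efficacy and safety summaries in the final report, and Protocol 10.2 and 10.2.6 call for such tables. If none is produced, that is itself a departure from the protocol.

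Second, final-dose grouping is in the protocol, the study is nonrandomised and mainly descriptive, and no dose hypothesis is tested. This also stands: the final-dose table is legitimate. But the protocol pairs it with a starting-dose table, and the SAP keeps only one of the two.

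Third, the effect may be small. Protocol 1.3.3 gives mean maximal antithrombin reductions of 83.6% on 50 mg and 85.9% on 80 mg in this study, which gives no support for a large gap in bleed rates. Protocol 1.5 says that the move from weight-based to fixed doses came early, and the first 28 days lie outside the primary efficacy period. By-year ABR and full adverse event listings also keep early events visible. All of this is fair.

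A reader might go further and infer that every dose-labelled figure is wrong, that the rule always loads 50 mg events onto 80 mg, or that the 50 mg group holds only people who never moved up. The documents do not support these readings. Only switchers are affected, and the rule works both ways, so anyone moved from 80 to 50 mg would bring 80 mg events into the 50 mg column. Nor do group sizes of 13 and 21 show how many switched.

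**Conclusion.** The point holds for dose-labelled ABR, adverse event and special-interest event summaries of the original dose period. There, events and person-time before a switch are attributed to the later dose, in either direction. The SAP also leaves out the protocol's starting-dose tables without listing the change.

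Overall, hemophilia-type and inhibitor tables, PK, post-pause data and parent-study adverse events are not affected, and no test or error rate is involved.

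The size cannot be stated. In the assumed scenarios the misattributed share of 80 mg person-time runs from 1.0% to 23.8%. The 80 mg ABR moves from 1.00 to between 1.02 and 1.48 with rates of 3 and 1, and not at all with equal rates. These figures rest on the 2017 group size, equal follow-up, and assumed numbers and timing of switches. They show a range of possibilities, not an estimate. It would be too strong to conclude that the reported dose results are materially biased.

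**What to change.** - In SAP 5.2, for dose-labelled ABR, adverse event and special-interest event summaries of the original period, assign events and person-days to the dose in force on the event date, splitting each participant at the switch.
- Say how switchers are counted. They appear in both dose columns, so adverse event denominators should be participants or person-time exposed to that dose. If a model is fitted by dose, it must allow for two records from one person.
- Note that the effect of a dose outlasts the injection: Protocol 1.5 cites antithrombin reduction for up to 60 days after a single dose. Events soon after a switch should be read with that in mind.
- Keep the final-dose table. Restore the starting-dose table, or list and justify its removal in SAP 2.7.
- Report the number of switchers, the direction of each switch, and their time on each dose. This alone would show whether the issue matters.

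The cost is SAP wording and a time-varying dose flag from existing dosing records. The SAP already uses the actual dose for PK, and SAP 6.10 already separates syringe and vial periods. No data collection or treatment changes.

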9.2.4 Adverse Event Reporting

The Investigator is responsible for reporting all AEs that are observed or reported from the first administration of study drug in this study, regardless of their relationship to study drug, through the follow-up visit.

All AEs must be fully recorded in the source records for the clinical study center and in the eCRF for the patient, whether or not they are considered to be drug related. Each AE must be described in detail: onset time and date, description of event, severity, relationship to investigational product, action taken, and outcome (including time and date of resolution, if applicable).

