10.2.6 Safety Analyses

Adverse events will be summarized by the MedDRA System Organ Class and Preferred Term. Incidence of treatment-emergent adverse events (TEAEs; those events that started after exposure to study drug or worsened in severity after dosing) will be presented by dose level and overall. Incidence of TEAEs will also be presented by maximum severity and relationship to study medication or underlying hemophilia. The incidence of SAEs and AEs leading to discontinuation of treatment will also be tabulated. By-patient listings will be provided for deaths, SAEs, and events leading to discontinuation of treatment.

Descriptive statistics will be provided for clinical laboratory data (including biochemistry, hematology, urinalysis, and coagulation) and vital signs data, presented as both actual values and changes from baseline relative to each on-study evaluation. Laboratory shift tables from baseline to worst values will be presented. Baseline will be defined as the last observation on or before Day 1. Abnormal physical examination findings, 12-lead ECG data, and antidrug antibody results will be presented in a by-patient data listing. Antidrug antibody results will also be tabulated.

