4 PARTICIPANT POPULATION

The following populations/analysis sets may be evaluated and used for presentation of the data.

Safety analysis set 1: All participants who receive at least a partial dose of study drug during the LTE14762 study under the original dose and regimen (ie, before the 2020 voluntary dose pause). The analysis set will be the main analysis set for analysis under original dose and regimen except for efficacy analysis and pharmacodynamics analysis.

Safety analysis set 2: All participants who receive at least a partial dose of study drug during the LTE14762 study under the revised dose and regimen (ie, after the 2020 voluntary dose pause). The analysis set will be used in safety analysis under revised dose and regimen. The analysis set will be the main analysis set for analysis under revised dose and regimen except for efficacy analysis and pharmacodynamics analysis.

Full analysis set 1: All participants in safety analysis set 1. The analysis set will be used in efficacy analysis and pharmacodynamics analysis under original dose and regimen.

Full analysis set 2: All participants in safety analysis set 2. The analysis set will be used in efficacy analysis and pharmacodynamics analysis under revised dose and regimen.

Per protocol set 1: All participants in the safety analysis set 1 who have no major protocol violations under the original dose and regimen in the following categories

- Failure to meet key eligibility criteria, which will be identified prior to database lock
- Prophylactic use of factor treatment or BPA (except for prophylaxis of bleeding in patients who require procedures or surgeries)

The protocol violation will be manually reviewed and adjudicated prior to database lock.

Per protocol set 2: All participants in the safety analysis set 2 who have no major protocol violations under the revised dose and regimen in the following categories

- Failure to meet key eligibility criteria, which will be identified prior to database lock
- Prophylactic use of factor treatment or BPA(except for prophylaxis of bleeding in patients who require procedures or surgeries)

The protocol violation will be manually reviewed and adjudicated prior to database lock.

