5.5 BASELINE DEFINITIONS

Baseline demographics and disease characteristics will be the baseline from both the parent study TDR14767(ALN-AT3SC-001) and study LTE14762. The following disease characteristics will be taken from the parent study:

- hemophilia type
- time since diagnosis
- biological phenotype
- prior treatment type
- historical ABR
- hepatitis C status
- historical ABR
- historical hemophilia clinic visit 6 months prior to parent study entry

Baseline assessment for by-visit analyses is defined as the last non-missing value on or before first significant Treatment Day and/or LTE14762 Study Day (ie, baseline on or before the first significant treatment day will be considered for all efficacy endpoints while baseline on or before the first LTE14762 study day will be considered for all safety endpoints). These baselines will be considered in analyses under both original and revised dose and regimen as main analysis.

An additional baseline under the revised dose and regimen is defined as the non-missing assessment on or prior to the revised dose re-start date regardless of dose regimen. It is applicable only for participant who consented to the protocol amendment 8. This baseline will be analyzed in selected safety endpoints under the revised dose and regimen. Detailed information will be specified in [Section 6.8](#).

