6.8.2 Adverse events

Adverse events (AE) analysis will include treatment-emergent events, with onset occurring in the LTE14762 study. (Note: All AEs collected in LTE14762 are considered TEAE because all participants received dose in TDR14767(ALN-AT3SC-001).)

All AEs will be coded using the MedDRA(version 25.1 or later) coding system and displayed in tables and data listings using system organ class (SOC) and preferred term (PT). AEs will be summarized by the numbers and percentages of participants reporting at least 1 AE, having at least 1 AE by primary SOC and PT. A participant with multiple occurrences of an AE will be counted only once in the respective AE category. Participants who report multiple occurrences of the same AE (preferred term) will be classified according to the most related or most severe occurrence, respectively.

All AE summaries will be summarized (frequency counts and percentages) by system organ class and/or preferred term, unless specified otherwise. The SOC will be presented according to

international standards (MedDRA Internationally Agreed Order), and the preferred term will be sorted within each SOC in decreasing order of frequency.

The following events are considered to be AEs of special interest (AESI):

1. ALT or AST elevations $>3 \times$ ULN
2. Suspected or confirmed thromboembolic events
3. Severe or serious injection site reactions (ISRs), ISRs that are associated with a recall phenomenon (reaction at the site of a prior injection with subsequent injections) or, those that lead to temporary dose interruption or permanent discontinuation of study drug.
4. Systemic (injection associated reactions (IARs), defined as hypersensitivity reactions which are related or possibly related to IMP.
5. Cholecystitis
6. Cholelithiasis

The identification of cholecystitis and cholelithiasis will be a combination of systematic search of higher level group term (HLGT) and AESI collected as it is in CRF. AEs whose HLT fall into the categories listed below will be considered as AESI of cholecystitis and cholelithiasis:

1. Bile duct disorders,
2. Gallbladder disorders
3. Hepatic and hepatobiliary disorders

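### The SAP ties the original-regimen safety start and safety baseline to the first dose of at least 20 mg in LTE14762, so for participants who started lower the baseline can fall after extension dosing began

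*SAP*

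**What the plan says.** **Passages that apply a 20 mg start to safety**

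- SAP 5.2 sets the threshold: "A significant dose is defined as any single dose of fitusiran that is greater than or equal to 20 mg". It then fixes the clock: "We also define Study Days in the LTE14762 study as the number of days from first significant dose in LTE14762". Figure 1 gives the safety start: "Starts from first significant dose of fitusiran in LTE14762 and in terms of study days".
- SAP 5.5 sets the reference value: "baseline on or before the first LTE14762 study day will be considered for all safety endpoints". SAP 6.8.3 to 6.8.5 run the original-regimen laboratory, vital-sign and ECG summaries from the LTE14762 study baseline up to the 2017 hold.

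**Passages that do not**

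- Protocol 10.2.6: "Baseline will be defined as the last observation on or before Day 1". Protocol 9.2.4 starts adverse event reporting at first dosing: "The Investigator is responsible for reporting all AEs that are observed or reported from the first administration of study drug in this study".
- For Safety analysis set 1, SAP 4 gives this membership rule: "All participants who receive at least a partial dose of study drug during the LTE14762 study under the original dose and regimen".
- SAP 6.8.2: "All AEs collected in LTE14762 are considered TEAE because all participants received dose in" the parent study.
- The body text of SAP 5.2 gives the 20 mg start to efficacy endpoints. Its next sentence bases safety on LTE14762 study data up to the restart, with no dose threshold.

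**Disclosure.** SAP 2.7 lists one departure from the protocol's statistical section, the efficacy analysis periods. SAP 2.6 mentions only an additional safety baseline after the 2020 pause.

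**The concern.** Long-term safety and tolerability is the primary objective. A potency threshold makes sense for bleeding and pharmacodynamic endpoints, because SAP 6.3 defines its periods by when AT lowering becomes therapeutic. The SAP gives no reason to carry the threshold over to safety.

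If the baseline is taken after the first extension doses, any laboratory, vital-sign or ECG change caused by those doses becomes part of the reference value. Later changes are then measured from the wrong point. The SAP also gives two answers to when safety analysis begins, so two programmers could produce different tables from the same data.

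**Working it through.** The plan gives no figure to reproduce on this point. The check is to chain the definitions and then see whether the documented starting dose can fall below the threshold.

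**1. The chain.** Significant dose = 20 mg or more (SAP 5.2). LTE14762 Study Day 1 = first significant dose in LTE14762 (SAP 5.2). Safety baseline = last non-missing value on or before Study Day 1 (SAP 5.5). So the safety baseline is the last value on or before the first dose of at least 20 mg in LTE14762, whatever lower doses came before it.

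**2. Can the starting dose be below 20 mg?** Protocol 6.5 expects a start at 0.225 mg/kg, and Protocol 1.5 says patients began on weight-based doses and moved to fixed doses early on.

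Cut-off weight = 20 mg ÷ 0.225 mg/kg = 88.9 kg.

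| Body weight | Dose at 0.225 mg/kg |
|---|---|
| 60 kg | 13.5 mg |
| 70 kg | 15.75 mg |
| 80 kg | 18.0 mg |
| 90 kg | 20.25 mg |

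At 0.45 mg/kg the cut-off is 20 ÷ 0.45 = 44.4 kg, so few adults would be below it. The issue concerns those who started at about 0.225 mg/kg.

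**3. What share of those starters?** The documents give no weights. *Assuming* normally distributed weights with mean 70 to 85 kg and SD 12 to 18 kg, the share below 88.9 kg runs from 94% (mean 70, SD 12) to 59% (mean 85, SD 18). This is a share of the 0.225 mg/kg starters, not of the study.

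**4. How late is Study Day 1?** With 30-day months (Protocol 1.5), *k* monthly doses below 20 mg delay it by 30*k* days: 30 days for one dose, 90 for three, 180 for six. The documents do not give *k*. For scale, the by-visit summaries stop at the 2017 hold. From first enrolment on 8 October 2015 (SAP 2.5) to 1 September 2017 (the hold date in SAP Table 4) is 694 days at most. One low-dose month is therefore at least 30 ÷ 694 = 4.3% of a participant's window, and three are at least 90 ÷ 694 = 13%.

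**5. What follows in the tables.**

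- *By-visit summaries.* SAP 5.10 assigns laboratory and vital-sign visits from the CRF label. A low-dose starter's CRF Day 1 or Month 1 can then precede his own baseline. The SAP does not say whether such visits are dropped or compared with a later reference.
- *ECG.* Protocol Table 1 schedules ECGs before the Day 1 dose and up to 24 hours after it, then none until Month 12. If the first dose of at least 20 mg fell between those visits, the last scheduled ECG before it would be the 24-hour recording after the first extension dose. Under the SAP chain, that post-dose recording would be the baseline.
- *Liver listing.* SAP 6.8.3 uses 3 × Baseline, meaning LTE14762 baseline, for participants abnormal at baseline. If that limb replaces the ULN limb for them, any rise during low-dose treatment raises the listing threshold in the same proportion.

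**The case against.** A reader might infer that early safety data are lost for lower-dose starters, or that early ALT rises are hidden. The documents do not support either reading.

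- *Adverse events.* SAP 6.8.2 counts every event collected in LTE14762, and all are listed. Figure 1 contradicts this but does not override it.
- *ALT and AST.* SAP 6.8.3 tabulates multiples of ULN at any time during LTE14762 and plots all central-laboratory values. SAP 6.8.2 treats elevations above 3 × ULN as events of special interest. Early elevations stay visible; only change from baseline is blurred.
- *By-visit summaries.* Because visits follow CRF labels, it is not established that the low-dose visits drop out.

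A reader might also infer that the 20 mg rule alone creates an on-drug baseline. It does not. All participants were dosed in the parent study. Parts C and D roll over about one month after their last parent dose, within the period of up to 60 days for which Protocol 1.5 says AT reduction lasts. Protocol Day 1 is not drug-naive either. What the rule adds is a baseline after *extension* dosing began.

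The strongest objection is that nobody may be affected, since SAP 2.1 says all participants initially receive 50 or 80 mg. That statement conflicts with Protocol 1.5 and 6.5, and the passages must be reconciled. It cannot settle the matter while SAP 5.2 itself provides for participants whose first significant dose came in LTE14762. SAP 5.10 adds that parent-study cohorts other than Parts C and D received relatively small doses.

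Finally, the lower-case study day in SAP 5.5 could be read as protocol Day 1. The SAP defines the term only by the 20 mg dose, so the text needs correcting either way.

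**Conclusion.** The plan is wrong as written and should be corrected. SAP 5.2 (Study Day and Figure 1) and 5.5 depart from the baseline in Protocol 10.2.6 without disclosing it. They also contradict the body text of SAP 5.2, Safety analysis set 1 and SAP 6.8.2.

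The effect is limited to participants who started LTE14762 below 20 mg. Within that group it touches change-from-baseline summaries of laboratory, vital-sign and ECG data, and the Baseline limb of the liver listing. Its overall size cannot be stated, because the documents give neither the number of such participants nor the length of the low-dose phase. The 88.9 kg cut-off rests on the protocol's expected 0.225 mg/kg start, and the 59% to 94% range rests on assumed weights.

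**What to change.** In SAP 5.2, Figure 1 and SAP 5.5:

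- Define LTE14762 Study Day 1 and the original-regimen safety start as the first LTE14762 dose of any size.
- Define the safety baseline as the last non-missing value on or before that dose.
- State that the 20 mg rule applies to efficacy and pharmacodynamics only.
- Align Figure 1 with the body text of 5.2 and with 6.8.2.
- Reconcile the starting-dose statement in SAP 2.1 with Protocol 1.5 and 6.5.

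It would help to report how many participants began LTE14762 below 20 mg and how long they stayed there. If the sponsor prefers to keep the 20 mg baseline for safety, SAP 2.7 should list it with a reason.

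The cost is SAP wording and one changed derivation. No new data are needed.
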